#### Follow-Up of Adverse Events and Serious Adverse Events

- The investigator is obligated to perform or arrange for the conduct of supplemental measurements and/or evaluations as medically indicated or as requested by the sponsor to elucidate the nature and/or causality of the AE or SAE as fully as possible. This may include additional laboratory tests or investigations, histopathological examinations, or consultation with other health care professionals.
- Once an AE is detected, it should be followed in the Adverse Events Form in the eCRF until it has resolved or until it is judged to be permanent; assessment should be made at each visit (or more frequently if necessary) of any changes in severity, the suspected relationship to the study treatment, the interventions required to treat the event, and the outcome.
- When the severity of an AE changes over time for a reporting period (eg, between visits), each change in severity will be reported as a separate AE.
- Updated SAE information will be recorded in the originally completed eCRF and reported to Incyte Pharmacovigilance (in the SAE EDC CRF) until resolution, stabilization, the event is otherwise explained, or the participant is lost to follow-up.
- Any updated SAE data (including SAEs being downgraded to nonserious) will be submitted to the sponsor (or designee) within 24 hours of receipt of the information.

### 9.4. Reporting of Serious Adverse Events

Regardless of suspected causality (eg, relationship to study treatment or study procedure[s]), all SAEs occurring after the participant has signed the main study ICF (ie, SAEs that occur during prescreening do not need to be reported) through at least 90 days after the last dose of study treatment **or** until the participant starts a new anticancer therapy must be reported to the sponsor (or designee) immediately, without undue delay but not later than within **24 hours** of obtaining knowledge of its occurrence unless otherwise specified by the Protocol. The investigator will submit any updated SAE data to the sponsor (or designee) immediately, without undue delay but not later than within 24 hours of it being available.

Investigators are not obligated to actively seek SAE information after the safety follow-up visit or more than 90 days after the last dose of study treatment. If the investigator learns of any SAE, including death, at any time during this period (disease status follow-up period), and they consider the event to be reasonably related to the study treatment or study participation, then the investigator must notify the sponsor (or designee) within 24 hours of becoming aware of the event.

After the initial AE/SAE report, the investigator is required to proactively follow each participant at subsequent visits/contacts. All SAEs will be followed until resolution, stabilization, the event is otherwise explained, or the participant is lost to follow-up (as defined in Section 7.3).

Prompt notification by the investigator to the sponsor regarding an SAE is essential so that legal obligations and ethical responsibilities for the safety of participants and the safety of a study treatment under clinical investigation are met.

If the SAE is not documented in the RSI of the [INCB099280 IB](#) or axitinib package insert ([Inlyta 2021](#)) for the study treatment (new occurrence) and is thought to be related to the study treatment, the sponsor or its designee may urgently require further information from the investigator for expedited reporting to health authorities. The sponsor or its designee may need to issue an Investigator Notification to inform all investigators involved in any study with the same

drug that this SAE has been reported. Suspected unexpected serious adverse reactions will be collected and reported to the competent authorities including EudraVigilance, as applicable, and relevant ethics committees following the sponsor's (or approved designee) SOPs in accordance with EU CTR No. 536/2014 and/or FDA CFR Part 312 or as per national regulatory requirements in participating countries.

The sponsor has a legal responsibility to notify both the local regulatory authority and other regulatory agencies about the safety of a study treatment under clinical investigation. The sponsor will comply with country-specific regulatory requirements relating to safety reporting to the regulatory authority, IRB/IEC, and investigators.

Investigator safety reports must be prepared for suspected unexpected serious adverse reactions according to local regulatory requirements and sponsor policy and forwarded to investigators as necessary.

An investigator who receives an investigator safety report describing an SAE or other specific safety information (eg, summary or listing of SAEs) from the sponsor will review and then file it along with the IB and will notify the IRB/IEC, if appropriate, according to local requirements.

#### **Serious Adverse Event Reporting**

- Information about all SAEs is collected and recorded on the Adverse Events Form in the eCRF.
- The investigator must report within 24 hours of learning of its occurrence any SAE via the EDC system (primary method) or by completing the Serious Adverse Event Report Form in English (only if the EDC system is not available). The contact information for Incyte Pharmacovigilance by email/fax is listed in the Study Reference Manual or the Incyte Reference Guide for Completing the Serious Adverse Event Report Form.
- In circumstances where the EDC system is not accessible for reporting SAE information (initial and/or follow-up SAE information) to the sponsor within 24 hours, refer to the Incyte Reference Guide for Completing the Serious Adverse Event Report Form. Once the EDC system is functional, the SAE report should be retrospectively added to the EDC system and follow-up should be completed through the EDC. The original copy of the Serious Adverse Event Report Form and the email or facsimile confirmation sheet must be kept at the study site (refer to the Incyte Reference Guide for Completing the Serious Adverse Event Report Form or Study Reference Manual for details and for the email address or fax number).
- Follow-up information is also recorded in the eCRF and transmitted to Incyte Pharmacovigilance via the EDC system. The follow-up report should include information that was not provided previously, such as the outcome of the event, treatment provided, action taken with study treatment because of the SAE (eg, dose reduced, interrupted, or discontinued), or participant disposition (eg, continued or withdrew from study participation). Each recurrence, complication, or progression of the original event should be reported as follow-up to that event, regardless of when it occurs.

### **9.5. Potential Drug-Induced Liver Injury**

In the event a participant has 1) an increase in ALT or AST elevation  $\geq 3 \times \text{ULN}$ , 2) a total bilirubin  $\geq 2 \times \text{ULN}$ , and 3) an ALP  $< 2 \times \text{ULN}$ , clinical tests (eg, blood and imaging tests) must be performed frequently as per standard of care until resolution and/or stabilization. In addition, a diagnostic workup must be performed to exclude alternative causes such as viral hepatitis, pre-existing chronic or acute liver disease or abnormalities, the administration of other drug(s) known to be hepatotoxic, or confirmed Hy's law.

Follow the SAE and follow-up reporting requirements per Section 9.2 as potential DILI AEs may be potential SAEs classified in the category of important medical event.

## 9.6. Events of Clinical Interest

Not applicable.

### 9.6.1. Adverse Events of Special Interest

Not applicable.

## 9.7. Emergency Unblinding of Treatment Assignment

Not applicable.

## 9.8. Pregnancy

Pregnancy, in and of itself, is not regarded as an AE unless there is suspicion that the study treatment may have interfered with the effectiveness of a contraceptive medication or method. When a pregnancy has been confirmed in a participant during maternal or paternal exposure to study treatment, the following procedures should be followed in order to ensure safety:

- The study treatment must be interrupted immediately.
  - If the female participant is no longer pregnant and meets the treatment continuation criteria within 28 days of the scheduled start of a cycle, study treatment may be resumed after approval has been received from the sponsor's medical monitor.
- The investigator must complete and submit the Incyte Clinical Trial Pregnancy Form to the sponsor or its designee within **24 hours** of learning of the pregnancy.

Data on fetal outcome are collected for regulatory reporting and drug safety evaluations. Follow-up should be conducted for each pregnancy to determine outcome, including spontaneous or voluntary termination, details of the birth, and the presence or absence of any birth defects, congenital abnormalities, or maternal and/or newborn complications, by following until the first well-baby visit. Pregnancy should be recorded on a Clinical Trial Pregnancy Form and reported by the investigator to the sponsor or its designee. Pregnancy follow-up information should be recorded on the same form. This form should include an assessment of the possible causal relationship to the sponsor's study drug to any pregnancy outcome, as well as follow-up to the first well-baby visit or the duration specified in local regulations, whichever is later. Refer to the Incyte Reference Guide for Completing the Clinical Trial Pregnancy Form or Study Reference Manual for further details.

**Any SAE occurring during the pregnancy of a study participant must be recorded and reported as described in Section 9.4.**

Abnormal pregnancy outcomes (eg, spontaneous abortion, fetal death, stillbirth, congenital anomalies, or ectopic pregnancy) are considered SAEs (if occurring in the study participant) and must be reported as described in Section 9.4. If an abnormal pregnancy outcome is reported in a

study participant's partner, the event should be reported to the sponsor on the Clinical Trial Pregnancy Form.

## **9.9. Warnings and Precautions**

Special warnings or precautions for the study drug, derived from safety information collected by the sponsor or its designee, are presented in the [INCB099280 IB](#). Additional safety information collected between IB updates will be communicated in the form of Investigator Notifications. Any important new safety information should be discussed with the participant during the study as necessary. If new significant risks are identified, they will be added to the ICF.

## **9.10. Product Complaints**

The sponsor collects product complaints on study drugs and drug delivery systems used in clinical studies in order to ensure the safety of study participants, monitor quality, and facilitate process and product improvements.

All product complaints associated with material packaged, labeled, and released by the sponsor or its designee will be reported to the sponsor. All product complaints associated with other study material will be reported directly to the respective manufacturer.

The investigator or their designee is responsible for reporting a complete description of the product complaint via email or other written communication to the sponsor contact or respective manufacturer as noted in the packaging information. Any AE associated with a product complaint should be recorded as described in [Section 9.3](#).

If the investigator is asked to return the product for investigation, they will return a copy of the product complaint communication with the product.

## **9.11. Treatment of Overdose**

Overdose is not an SAE unless it meets the criteria of an SAE (see [Section 9.2](#)).

For this study, any dose of INCB099280 or axitinib greater than the dose prescribed within a 24-hour time period will be considered an overdose and recorded in the eCRFs.

In the event of an overdose, the investigator/treating physician should do the following:

- Contact the medical monitor immediately.
- Closely monitor the participant for any AE/SAE and laboratory abnormalities until study treatment can no longer be detected systemically (at least 90 days).
- Obtain a plasma sample for PK analysis within 2 days from the date of the last dose of study treatment if requested by the medical monitor (determined on a case-by-case basis).
- Document the quantity of the excess dose as well as the duration of the overdose in the eCRF.

Decisions regarding dose interruptions or modifications will be made by the investigator in consultation with the medical monitor based on the clinical evaluation of the participant.

There has been no clinical experience with overdose of INCB099280. Treatment of overdose should consist of general supportive measures.

There is no specific treatment for axitinib overdose. In a controlled clinical study with axitinib for the treatment of patients with RCC, 1 participant inadvertently received a dose of 20 mg BID for 4 days and experienced dizziness (Grade 1; [Inlyta 2021](#)). In clinical studies, participants who received up to 10 mg BID or 20 mg BID experienced adverse reactions that included hypertension, seizures associated with hypertension, and fatal hemoptysis ([Inlyta 2021](#)). In cases of suspected overdose, axitinib should be withheld and supportive care instituted.

## 10. STATISTICS

This section outlines the statistical analysis strategy and procedures for this study. If changes are made to primary efficacy and safety and/or secondary efficacy hypotheses or the statistical methods related to those hypotheses after the study has begun but before the final database lock, the Protocol will be amended, consistent with ICH E9 ([1998](#)) and ICH E9(R1) ([2021](#)). The detailed statistical analyses will be documented in the Statistical Analysis Plan.

### 10.1. Sample Size Determination

The study will be conducted in 2 parts: dose finding in Part 1 and dose expansion in Part 2. In Part 1 of the study, approximately 12 participants with previously treated advanced clear cell ovarian cancer, rare histological subtype epithelial cancers of the gynecological tract, endometrial cancer, or cervical cancer who have received at least 1 prior line of systemic chemotherapy and are not candidates for curative surgery or (chemo)radiation will be enrolled in dose finding of INCB099280 administered at 400 mg BID in combination with axitinib to determine the safety and tolerability of the combination therapy and identify the RDE. A hybrid of a modified mTPI design and a dose-toxicity model will be used to make dose decisions.

In Part 2, up to 30 participants will be enrolled in each of the 4 disease cohorts to further evaluate the safety and tolerability of the combination therapy as well as to continue characterizing the PK and antitumor activity.

With 30 participants in a cohort-specific dose group, the probabilities of observing different numbers of events with true rates of 0.05, 0.1, 0.2, 0.25, 0.3, 0.35, 0.4, and 0.5 are listed in [Table 20](#). This calculation is applicable to detecting events of DLTs, objective responses, Grade 3 or higher TEAEs, etc.

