#### 4.1.1. Part 1: Dose Finding

Participants with diagnoses as defined for all disease-specific cohorts may be enrolled in Part 1. During the dose-finding part of the study, up to 2 doses of axitinib administered in combination with INCB099280 will be evaluated to identify a dose for further evaluation in the dose-expansion phase of the study.

The starting doses (Dose Level 1) are INCB099280 400 mg BID and axitinib 5 mg BID (see Section 2.3 and Section 2.4.2 for further details). Up to approximately 12 participants will be enrolled in this part of the study.

Dose levels, based on Dose Level 1 tolerability, are illustrated in Figure 4.

Dose Level –1 will only be investigated if a dose de-escalation rule is met at Dose Level 1 (see Section 6.5.2).

[figure not shown]
Decisions on dose will be based on DLTs observed in participants during the first 3 weeks of treatment (see Section 6.5).

No intraparticipant dose escalation of either of the study drugs will be permitted.

Dose finding may conclude after one of the following:

1. At least 9 DLT-evaluable participants have been enrolled in a dose level and with a hybrid design decision rule of "stay" met (see Table 5); then the highest dose with an observed DLT rate no higher than the target toxicity rate of 30% will be treated as the preliminary MTD.
2. At least 3 DLT-evaluable participants have been enrolled in Dose Level 1 and with a hybrid design decision rule of "escalate" met (see Table 5); then Dose Level 1 is considered safe and tolerable, and the MTD has not been reached.
3. At least 3 DLT-evaluable participants have been enrolled in Dose Level –1 and with a hybrid design decision rule of either "de-escalate" or "eliminate" met (see Table 5); then none of the dose levels will be considered safe and tolerable.

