**Table 22: Populations for Analysis**

Population	Description
FAS	The FAS includes all study participants who received at least 1 dose of either study treatment. The FAS will be used for the summary of demographics, baseline characteristics, participant disposition, and overall efficacy analyses. Participants will be analyzed according to the dose to which they have been assigned.
Safety-evaluable	The safety-evaluable population includes all participants who received at least 1 dose of either study treatment. All safety analyses will be conducted using the safety-evaluable population. Treatment groups for this population will be determined according to the actual dose the participant received regardless of assigned dose.
DLT-evaluable	The DLT-evaluable population includes participants enrolled into Part 1 who received at least 75% of the planned doses of INCB099280 and axitinib (ie, 32 doses of INCB099280 and axitinib) at the level assigned during the DLT observation period or have had a DLT during the 3-week DLT observation period. DLT-evaluable participants will be summarized independently.
PK-evaluable	The PK-evaluable population includes all participants who received at least 1 dose of either study treatment and have provided at least 1 postbaseline sample for PK analysis.
Pharmacodynamic-evaluable	The pharmacodynamic-evaluable population includes all participants who received at least 1 dose of either study treatment and have provided a baseline sample and at least 1 postbaseline plasma sample for pharmacodynamic analysis.
PK/pharmacodynamic-evaluable	The PK/pharmacodynamic-evaluable population includes all participants who are both PK-evaluable and pharmacodynamic-evaluable.

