#### 10.4.2. Safety Analyses

The clinical safety data (eg, vital signs, ECGs, routine laboratory tests, AEs) will be summarized using descriptive statistics (eg, mean, frequency) for the safety-evaluable population. Safety analyses will be provided for each dose for Part 1 and Part 2. An analysis of the combined doses will also be provided for Part 1 and Part 2.

The DLT incidence rate along with a 90% CI based on exact binomial distribution will be provided for each dose level using the DLT-evaluable population. The participants with DLTs and the type of DLT will be listed by dose level.

The tolerability of study drug will be assessed by summarizing the number of participants with a TEAE leading to dose interruptions, dose reductions, and treatment discontinuations for either study drug.

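### Section 10.1 extends the n = 30 event probabilities of Table 20 to DLTs, but DLTs are analysed only in Part 1, where no group can reach 30

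*Protocol*

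**What the plan says.** Section 10.1 places the group of 30 in Part 2: "In Part 2, up to 30 participants will be enrolled in each of the 4 disease cohorts". The probability statement opens with "With 30 participants in a cohort-specific dose group", and the "true rates of 0.05, 0.1, 0.2, 0.25, 0.3, 0.35, 0.4, and 0.5 are listed" in Table 20. The section then sets the scope of the table: "This calculation is applicable to detecting events of DLTs, objective responses, Grade 3 or higher TEAEs, etc".

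The rest of the protocol ties DLTs to Part 1:

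- Tables 1 and 4 list DLT occurrence only under the Part 1 primary safety objective. The Part 2 safety objective lists TEAEs and TEAEs leading to dosing modification.
- Table 22: "The DLT-evaluable population includes participants enrolled into Part 1".
- Section 10.4.2: the DLT rate and its 90% CI "will be provided for each dose level using the DLT-evaluable population".
- Section 4.1.1, on the size of Part 1: "Up to approximately 12 participants will be enrolled in this part of the study". On how those participants may be divided: "up to 2 doses of axitinib administered in combination with INCB099280 will be evaluated".

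**The concern.** The sentence credits the design with a detection property for DLTs that it does not have. The table rests on 30 participants in one group. The population in which DLTs are counted has about 12 in total, and these may be divided between two dose levels. At low true rates the difference is large.

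What is at stake is how the sample-size section is read. DLT occurrence is a Part 1 primary endpoint, and this is the only figure on DLT detection in Section 10.1. A reader who takes the sentence at its word would credit Part 1 with more sensitivity to uncommon DLTs than it has.

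**Working it through.** **Inputs.** Table 20: n = 30, true rates p from 0.05 to 0.5 (Section 10.1). Part 1: up to about 12 participants, up to two dose levels (Section 4.1.1). DLT analysis: per dose level, Part 1 participants only (Table 22, Section 10.4.2).

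**Step 1: reproduce Table 20.** For at least one event, P = 1 − (1 − p)^n. With n = 30:

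- p = 0.05: 1 − 0.95^30 = 78.5%
- p = 0.10: 1 − 0.90^30 = 95.8%
- p = 0.30: 1 − 0.70^30 > 99.9%

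These match the first row as printed. That row is labelled > 1 event, but read literally P(X > 1) at p = 0.05 is 44.6%, which is the figure in the second row. All five rows reproduce from the exact binomial tail P(X ≥ r) with r = 1, 2, 5, 10 and 15. So the labels should carry ≥ rather than >, and 78.5% is the chance of at least one event. The comparison below uses that reading.

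**Step 2: which group sizes can occur for DLTs.** The upper end is 12, if every Part 1 participant is treated at one dose level. The lower end is 3: Section 4.1.1 lets dose finding conclude after at least 3 evaluable participants at Dose Level 1 if the rule to escalate is met, and Table 5 gives that rule for 0 DLTs in 3. The protocol does not fix the split between dose levels, so 3 to 12 is an assumed range. The columns of Table 5 stop at 15 evaluable participants, half of 30.

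**Step 3: the same formula at the Part 1 sizes.** Chance of at least one DLT:

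| n | p = 0.05 | p = 0.10 | p = 0.30 |
|---|---|---|---|
| 30 (Table 20) | 78.5% | 95.8% | > 99.9% |
| 12 | 46.0% | 71.8% | 98.6% |
| 9 | 37.0% | 61.3% | 96.0% |
| 6 | 26.5% | 46.9% | 88.2% |
| 3 | 14.3% | 27.1% | 65.7% |

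**Step 4: the gap.** At n = 12, Table 20 is higher by 78.5 − 46.0 = 32.5 points at a 5% rate and by 95.8 − 71.8 = 24.0 points at 10%. At the 30% target toxicity rate the gap at n = 12 is only a little over 1 point (> 99.9% against 98.6%). At n = 3 it is more than 34 points even at the 30% rate (> 99.9% against 65.7%).

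For at least two events, Table 20 gives 44.6% and 81.6% at rates of 5% and 10%. At n = 12 the figures are 11.8% and 34.1%, which are 32.8 and 47.5 points lower.

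**The case against.** The best defence has four parts.

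- **The table shows its own n.** Table 20 is headed with a sample size of 30, the text around it repeats the number, and Section 10.1 gives the Part 1 size just before. The sentence could be read as naming kinds of binary event that an n = 30 calculation would suit. This stands in part: the protocol never prints a DLT detection probability for Part 1. But the sentence says the calculation applies to DLTs, and no group of 30 in which DLTs are analysed exists.
- **DLT criteria are checked more widely.** Section 4.1 says, for the study as a whole, that adverse events are assessed against the DLT criteria. That creates no Part 2 DLT endpoint or population; Tables 1, 4 and 22 still confine both to Part 1.
- **Nothing operational depends on it.** Dose decisions use Table 5, the DLT rate is reported with an exact 90% CI in the proper population, and Section 10.3 rules out formal tests. This stands in full and limits the importance of the point.
- **Part 1 was not sized to detect DLTs at 5%.** This also stands. The rules target a 30% rate, where 12 participants at one dose level do almost as well as 30. The reassurance does not extend to a dose level with 3 or 6 participants.

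A reader might also infer that Table 20 is miscalculated, or that Part 1 is too small for its purpose. The documents support neither. The table's values are exact for n = 30, and the protocol does not offer detection probability as the basis for the size of Part 1.

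**Conclusion.** The point holds as an error in a stated operating characteristic, and it is minor. The scope given to Table 20 in Section 10.1 contradicts the protocol's own definition of where DLTs are counted. Applied to DLTs, the table overstates the chance of seeing at least one by 32.5 points at a 5% true rate and 24.0 points at 10% if all 12 are at one dose level, and by more at smaller groups. At the 30% target rate the overstatement is negligible at n = 12 and substantial only when a dose level has few participants.

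These figures assume independent participants with a common DLT rate, every enrolled participant DLT-evaluable, and the 3-to-12 range described above. It would go too far to conclude that dose selection or participant protection in Part 1 rests on the wrong number; it rests on Table 5.

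**What to change.** In Section 10.1, delete DLTs from the sentence after the list of true rates, so that Table 20 is offered only for Part 2 events such as objective responses and TEAEs of Grade 3 or higher.

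If the sponsor wants a DLT detection figure, add one line for the Part 1 sizes. For example: with 3, 6, 9 or 12 evaluable participants at a dose level, the chance of at least one DLT is 14.3%, 26.5%, 37.0% or 46.0% at a true rate of 5%, and 65.7%, 88.2%, 96.0% or 98.6% at 30%. This line is optional; the deletion alone removes the contradiction.

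While editing, change the Table 20 row labels from > to ≥, since the printed values are for at least r events.

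The cost is one sentence. No sample size, decision rule or analysis changes; the only effect is that the stated detection property for DLTs is withdrawn or becomes less favourable.
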